3.4. Interventions

Each participant will be subjected to four interventions: a standard lancet prick, a jet injection with a standard circular orifice, and two jet injections with different custom slot orifices. These interventions will be performed on the side of the fingertip of the middle (3rd finger) and ring finger (4th finger) of either hand. Which finger receives which intervention will be randomised, as will the order of the interventions. The participants will be blinded by an opaque barrier which will prevent them observing the procedure but allow them to see and communicate with the practitioner. After each intervention has been applied, and the associated blood samples collected, there will be a 2 minute 'break' before performing the next intervention. The participants will be shown the jet injector and lancing device following the procedures. The interventions will be identical for both groups with the exception of the fluorescent dye (ICG, 0.01 mg/L) added to the jet injected fluid for group 2.

Lancet

Capillary blood will be sampled in accordance with the "WHO guidelines on drawing blood" [8]. This will involve a lancet piercing the skin to a depth of 2.3 mm. The collection of the blood into four sequentially-collected samples differs from the WHO guidelines, but is necessary to the study (see section 3.5), and adds no extra risk to the participant.

Jet Injection

A jet injection of less than 50 μ L of sterile isotonic saline will be performed to pierce the skin. The jet will target the same depth in the dermis as the lancet (2.3 mm). Similarly to the lancet, the jet injector based blood sampling will be done as closely as possible to the WHO guidelines. However, the use of a jet injector itself is not currently within these guidelines, as this is novel to this study.

For group 2 ICG will be added to the injected saline to a concentration of (10 mg/L). An ICG concentration of 10 mg/L is well below the dose used for other diagnostic procedures (5 g/L) approved by the FDA.

3.5. Blood collection

The blood released at the intervention site will be collected at four time points following the intervention: 10 s, 20 s, 30 s and 40 s. Massaging or squeezing of fingers will be performed in accordance with the "WHO guidelines on drawing blood" before each collection. The amount of massaging or squeezing of fingers will be independent of the amount of blood observed at the intervention site. The collected blood will be separated into different sample containers based on these intervals. Hence, each intervention will be associated with four blood samples (a total of 16 blood samples per participant). We are collecting blood in this way to allow us to observe the time-related behaviour of blood release and glucose concentration following breaking the skin. This is important to research question (b) (section 2.1).

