This work will test the ability of a needle-free jet injection device to release capillary blood in order to measure glucose concentration. We wish to evaluate how this technique compares to the current best practice where the skin is broken with a lancet. We will compare jet injections performed with a standard circular orifice and two custom orifices that produce jets of rectangular shape ('slot' orifices). The custom slot orifices are designed to mimic the shape of the puncture made by a lancet in the skin, and we hypothesise that this may assist in obtaining a blood sample with the jet injector. The comparisons will require measurement of the volume of blood released, blood sample dilution, blood glucose concentration, and participant discomfort.

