3.1. Study Design Overview

This is a pilot study aiming to assess the feasibility of using a jet injector in the place of a lancet when retrieving a capillary blood sample. Each participant in the study will receive four interventions: the current best practice for capillary blood sampling (a lancet prick), a jet injection with a standard circular orifice, and two jet injections with different custom slot orifices. This study is designed to be single-blinded and all participants will serve as their own control as each participant will receive the lancet based sampling. Participants will be aware they are receiving one of each intervention, but will be blinded to the order and identity of which intervention is occurring at which site. The study will be conducted in the ground floor laboratory space (G20) of the Auckland Bioengineering Institute ([name]).

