3.2. Population & Recruitment

We intend to recruit up to 35 healthy participants to take part in this study. These participants will be divided into two groups with up to 25 participants in the first group and up to 10 in the second. The difference between these groups relates to the measurements that will be made on their blood samples, and also in the injectate used to obtain these measurements. The samples gathered from participants in the first group, using isotonic saline for the jet injections, will be tested for glucose concentration, while those from the second group, using isotonic saline with ICG for the jet injections, will have a fluorescent based dilution measurement. Participants will be aware that the study is structured in this way, and will be aware of which group they are being recruited into.

With a minimum sample size of 20 in the first group we predict we will be able to distinguish statistically significant differences between groups whose mean dilution differs by as little as 10% ($\sigma_{glucometer}$ =0.6 mmol/L, α =0.05, β =0.1). We predict we will be able to observe differences in mean dilution as low as 5% in group 2 with a sample size of at least 8 ($\sigma_{fluorimeter}$ =3%, α =0.05, β =0.1). Sample volume is measured identically across both groups and we predict we will be able to observe differences in mean volume released as low as 0.84 µL ($\sigma_{BloodVolume}$ =1 µL, α =0.05, β =0.1).

The study will be advertised within the Auckland Bioengineering Institute and Department of Engineering Science. This will involve flyers posted within Auckland Bioengineering House ([name]) and an email sent to the Auckland Bioengineering Institute. These advertising materials will recommend that anybody interested in participating get in contact with the researchers for more information. In response to expressions of interest the researchers will provide a copy of the participant information sheet (PIS) and consent form (CF) to give detailed information about the study. Participants will be asked to take their time reading these forms and, if they are interested in participating, to indicate times that might suit them to come in for the study. This will also allow potential participants adequate opportunity to ask questions and seek external advice regarding participation in the study.

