3.8. Personnel

Our research team includes experts in needle-free drug delivery (bioengineers) and [name], who provides clinical oversight. In addition, a healthcare professional trained in phlebotomy (e.g. nurse) will be employed to oversee the blood sampling procedures.

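### Squeezing effort is made independent of the blood seen but not of the device, so the volume comparisons in questions (a) and (c) are open to operator bias

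*Protocol*

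**What the plan says.** - **Squeezing (Protocol 3.5).** Blood is collected at 10, 20, 30 and 40 s after every intervention. "Massaging or squeezing of fingers will be performed in accordance with the 'WHO guidelines on drawing blood' before each collection". The next sentence is the safeguard: "The amount of massaging or squeezing of fingers will be independent of the amount of blood observed at the intervention site". Section 3.4 says that sampling after jet injection will also keep as near to the WHO guidelines as possible.
- **Blinding (3.1, 3.4).** "This study is designed to be single-blinded and all participants will serve as their own control". The means is a screen for the participant: "The participants will be blinded by an opaque barrier which will prevent them observing the procedure". No masking of the person who squeezes or collects is described.
- **Allocation (3.4).** "Which finger receives which intervention will be randomised, as will the order of the interventions".
- **Personnel (3.8).** "a healthcare professional trained in phlebotomy (e.g. nurse) will be employed to oversee the blood sampling procedures". The protocol does not name who squeezes.
- **Outcome (2.1, 3.6).** Volume is read from the filled length of the capillary tube. It answers question (a), jet versus lancet, and the first part of (c), slot versus circular.
- **Expectation (2. Research Aims).** Of the slot orifices: "we hypothesise that this may assist in obtaining a blood sample with the jet injector".
- **Precision (3.2).** The plan expects to observe "differences in mean volume released as low as 0.84 µL", with an SD of 1 µL, α = 0.05 and β = 0.1.

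**The concern.** The volume outcome is partly produced by the hands of the person collecting it. The protocol accepts this implicitly, since a rule separating effort from the blood seen would otherwise have no purpose. That rule closes one route to bias, squeezing harder when little blood appears. It leaves a second route open: effort that differs, perhaps unconsciously, because the operator knows which device was used.

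The rest of the design does not close that route. The screen faces the participant. Randomising finger and order balances site and sequence, but handling that follows the device occurs after allocation and stays with the device. A larger sample only estimates the biased difference more precisely.

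A systematic difference in effort would be read as a device effect. In question (c) it could create or exaggerate an advantage for either orifice type. In question (a), which asks whether volumes are similar, it could also hide a real difference. This is conduct at the point of measurement, so no later analysis can repair it.

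**Working it through.** **1. Which routes to bias are closed**

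| Possible source of unequal effort | Addressed in the protocol? |
|---|---|
| Number and timing of squeezing episodes | Yes: before each of four common time points (3.5) |
| General technique | By reference to the WHO guidelines (3.4, 3.5), whose content is not available here |
| Amount of blood seen | Yes, by rule (3.5), though with no stated count or duration against which to check it |
| Finger and order | Yes, randomised (3.4) |
| Knowledge of the device | No |
| Massage or squeeze; count and duration within each interval | Not stated in the protocol |

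**2. Does the person squeezing know the device?** This is inferred. Blinding is single, by a screen for the participant, and nothing hides the device from the practitioner. A lancing device and a motor-driven injector can hardly be confused. For slot versus circular the inference is weaker, although section 3.7 describes different hardware: single-use circular ampoules in sterile packaging, and custom slot ampoules that are reused.

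**3. Reproducing the plan's 0.84 µL**

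Inputs from 3.2: SD 1 µL, α = 0.05 (sidedness not stated; two-sided assumed), power 0.90, minimum sizes 20 and 8 (28 pooled, since volume is measured identically in both groups), maximum 35. The protocol states no n beside the volume figure.

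Detectable difference = (1.960 + 1.282) × SD × √(2/n), unpaired normal approximation:

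- n = 28: 3.242 × 0.2673 = 0.866 µL
- n = 30: 3.242 × 0.2582 = 0.837 µL
- n = 35: 3.242 × 0.2390 = 0.775 µL

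The stated figure is reproduced approximately and is not in dispute.

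**4. Illustration of size**

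Section 3.6 expects samples of about 5 µL, so 0.84 µL is 0.84 / 5 = 16.8% of a typical sample.

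Assumptions that are not in the documents: volume is proportional to effort; effort differs systematically between two devices by the percentage shown; 0.84 µL refers to a single sample.

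| Effort difference | Shift in volume | Share of 0.84 µL |
|---|---|---|
| 5% | 5 × 0.05 = 0.25 µL | 30% |
| 10% | 5 × 0.10 = 0.50 µL | 60% |
| 20% | 5 × 0.20 = 1.00 µL | 119% |

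With no true device difference and a shift b, the chance of a significant result is Φ(b/SE − 1.96) + Φ(−b/SE − 1.96), where SE = √(2/n) for an SD of 1 µL, using the same unpaired model:

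- n = 28 (SE 0.267): 15.5% for b = 0.25 µL; 46.5% for b = 0.50 µL
- n = 35 (SE 0.239): 18.2% for b = 0.25 µL; 55.2% for b = 0.50 µL

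The nominal rate is 5%. The rates rise with n, which shows that recruiting more participants does not help.

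**The case against.** The strongest reply is that the protocol already controls the squeezing. It applies one external guideline to lancet and jet alike, fixes the same four time points for every intervention, and forbids the most obvious adjustment, responding to the blood seen. A detailed routine often sits in a working procedure, and this is a pilot feasibility study.

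Much of that stands. A reader might infer that technique is left wholly to choice at each of the 16 collections. The documents do not support this: the number and timing of squeezing episodes are common to all devices, and how far the WHO guidelines fix the rest cannot be judged here. What can be said is that the protocol itself states no count or duration and does not choose between the two actions.

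A reader might also take it as fact that the operator knows the device. The protocol never says who squeezes, so this remains an inference. The slot hypothesis should not be hardened either: the protocol says that the shape may help in obtaining blood, not that it will release more.

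Nor do the documents establish a separate device operator, or a second person at the site free to collect blind. Section 3.4 mentions a practitioner, and section 3.8 a professional who oversees sampling. A remedy that relies on two existing roles would go too far.

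The reply does not answer the remaining gap. Nothing asks for effort to be independent of the intervention, and no routine written in the protocol would make that independence visible.

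**Conclusion.** The point holds as a limited, inexpensive improvement. The safeguard in 3.5 is sound as far as it goes, but it covers the blood observed and not the device. With only participants described as blinded, the volume comparisons in (a) and (c) are open to operator bias, more plainly so for lancet versus jet than for slot versus circular.

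The stronger conclusion, that the volume results will be biased or will favour the slot, is not supported. Neither the direction nor the size of any bias can be derived from the documents. The 10% illustration, 0.5 µL or about 60% of the detectable difference, rests on an assumed effort difference, assumed proportionality, and reading 0.84 µL as a per-sample figure, which 3.2 does not say. The false-positive rates rest additionally on the unpaired model and the SD of 1 µL. Together they show only that a modest systematic difference in handling would be large enough to matter against the precision the plan claims.

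**What to change.** In section 3.5, keep the reference to the WHO guidelines and the four time points, and revise the safeguard so that:

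1. squeezing effort is independent of both the blood observed and the intervention;
2. one scripted action is used, either massage or squeeze, with the same count and duration before every collection, paced by a timer;
3. the same operator does this at all four sites of a participant.

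This costs one paragraph, a timer, brief training and slightly less flexibility at collection. It needs no extra staff and leaves the interventions and collection times unchanged.

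Conditional addition: if staff already present allow it, the person who squeezes and collects should not watch the device being selected and fired. The handover would have to fit within the first 10 s. Masking would be incomplete, because injectate or the shape of the puncture may reveal the device, so it should support the scripted routine and not replace it.

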3.6. Measurements

Volume

The blood will be collected from the skin using capillary tubes. As the dimensions of these capillary tubes are known the sample volume will be measured by the length of tube that is filled with blood.

Group 1: Glucose Concentration

For the samples collected on participants from group 1 we will then measure the glucose concentration of each blood sample. This will be done using a CareSens N point of care glucometer. This approved (and Pharmac funded) device involves the blood sample being collected onto a single use test strip inserted into the glucometer. The dilution of the blood samples collected following the jet injections will be implied by comparing the glucose concentration with that measured on the control (lancet) samples. The blood samples will be disposed of as medical waste following this glucose measurement.

Group 2: Blood Dilution (Fluorescence)

For group 2 after the volume is measured, we will measure the ICG concentration in the sample using a benchtop fluorimeter that has been developed at the Auckland Bioengineering Institute specifically for this purpose. The capillary tube containing the blood sample will be placed into the fluorimeter, which will excite the sample with 780 nm light. The resulting fluorescence will be measured, indicating the concentration of ICG and hence the proportion of injectate in the blood sample.

As the fluorimeter requires a sample of 10 μ L to produce a reliable measurement, and we expect our samples to typically be around 5 μ L, we will pre-mix the samples with isotonic saline solution. We will mix a volume of saline rounded up to the nearest 1 μ L with our sample to ensure a total volume of at least 10 μ L. In samples where the initial volume is greater than 5 μ L the added volume of saline will be equal to the sample volume rounded up to the nearest 1 μ L. This will ensure all samples will end up in the ideal concentration range of 0 mg/L – 5 mg/L for measurement of ICG with this device. The samples will be weighed following this mixing to quantify the volume that was added. The fluorescence measurement, initial sample volume, and mixed volume will then be used to calculate the ICG concentration, and therefore the blood volume, in the initial sample.

Perceived Pain

After each intervention and its associated blood collection, the participant will be asked to score the pain associated with the intervention on a standard verbal numeric rating scale. Each participant will be asked to rate the pain experienced from 0-10, with zero representing no pain, and 10 representing extremely severe pain. After 24 hours following the interventions, the participants will be asked to complete a questionnaire to re-assess the level of pain and any swelling, redness, bruising or soreness they have perceived at each intervention site.

Site Reactions

After blood samples are collected for each intervention, a sterile cotton-wool ball will be applied until bleeding stops. A microscope image of the intervention site will be taken immediately after the bleeding has stopped. This will reveal whether each intervention site results in a visible wound. The participants will be asked to take a photograph of each of the intervention sites, and answer some questions regarding their fingertips, 24 hours after receiving the interventions. The questions will reveal any persisting discomfort or reactions at the intervention sites, and the pictures will give the researchers an indication of any swelling and/or redness.

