While blood extraction with a jet injector has not yet been trialled, one study investigated the ability of a jet injector to extract interstitial fluid [4]. This study attempted to collect the fluid back through the same small orifice through which the jet was formed, and waited less than 0.5 seconds between breaking the skin and collecting the fluid. The volume of fluid collected ranged between 10 μ L and 40 μ L but was found to be mainly derived from the fluid that was injected, with interstitial fluid making up between 1% and 3%. As demonstrated by this study, we anticipate that one of the major problems with obtaining a capillary blood sample using jet injected fluid. As part of this study we wish to investigate the extent of this dilution issue. We propose to measure the dilution by marking our injected fluid with indocyanine green (ICG), an FDA approved fluorescent marker. By exciting the retrieved blood samples with 780 nm light, and measuring the resulting fluorescence we will be able to measure the dilution of the sample.

ICG is commonly used for diagnostic purposes (e.g., cardiocirculatory, retinal and liver function diagnostic tests), typically at a dose of no more than 2 mg/kg and a concentration of 5 g/L [5]. ICG has been delivered transdermally into the subcutaneous tissue in multiple fluorescent lymphography studies, and into the dermal layer in a recent study performing fluorescent microscopy. Delivery of 20 μ L of 5 g/L ICG into the dermis was described as having a "short-time tolerable burning sensation" [6], but in this study we plan to use a concentration of only 10 mg/L.

2. Research Aims

In this study we intend to use needle-free jet injection not to deliver a drug, but instead just to pierce the skin with a small volume of isotonic saline or ICG solution, and then retrieve a capillary blood sample. Ultimately we believe a single jet injection device may be able to extract blood, perform a blood glucose measurement and then, based on this measurement, deliver the ideal volume of insulin. However, this study will focus only on establishing the ability of this technique to achieve a measurement of blood glucose concentration.

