2.1. Principal Research Question

"Can a needle-free jet injection device be used to obtain a capillary blood sample for a glucose concentration measurement?"

This can be broken down into five further questions which relate directly to the measurements we will be making:

- a) Does a jet injector release a similar volume of capillary blood relative to a lancet?
- b) Does the use of a jet injector dilute the capillary blood sample, and, if so, how does this dilution change over time as blood is released?
- c) Does a slot orifice help release more blood than a circular orifice? And is the dilution of the collected blood different for jet injection with a slot orifice versus a circular orifice?
- d) Is the use of a jet injector for this purpose associated with similar, or lesser, levels of discomfort relative to a lancet?
- e) Does a jet injection lead to any significantly different skin reactions at the intervention site relative to a lancet prick?

3. Research Methods

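### In Group 1 and in any pooled comparison, tube volume counts returned saline as blood at jet sites but not at lancet sites, with no stated conversion to blood volume

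*Protocol*

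**What the plan says.** Protocol section 2.1, question (a), asks: "Does a jet injector release a similar volume of capillary blood relative to a lancet". Question (c) asks whether a slot orifice releases more blood than a circular one and, separately, whether dilution differs between them. Both volume questions concern blood.

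Section 3.6 fixes the measurement: "the sample volume will be measured by the length of tube that is filled with blood". Section 3.2 adds "Sample volume is measured identically across both groups" and states that the study can "observe differences in mean volume released as low as 0.84 µL" (SD "1 µL, α =0.05, β =0.1"). No sample size is attached to that figure. The minima given nearby are "With a minimum sample size of 20 in the first group" and, for Group 2, "with a sample size of at least 8".

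By sections 3.4 and 3.6, each jet site receives under 50 µL of saline, lancet sites receive none, and a typical sample is expected to be about 5 µL.

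Dilution is handled differently in the two groups (section 3.6). In Group 2, fluorescence, initial volume and mixed volume are used to calculate the ICG concentration and, from it, the blood volume of the initial sample. In Group 1, dilution is inferred by comparing jet glucose with lancet glucose, but the text does not carry that result over to volume.

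**The concern.** The quantity measured and the quantity asked about coincide at lancet sites but not at jet sites. Any saline that returns to the skin surface lengthens the filled part of the tube and, unless removed, is counted as blood released by the jet. A jet that releases less blood than the lancet could then appear similar, and one that releases the same amount could appear to release more. Because the error is systematic, a larger sample does not reduce it; it only makes a wrong conclusion look more certain.

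The protocol itself expects injectate in the samples. Question (b) is about dilution, Group 1 is sized to detect a 10% difference in dilution, and the Background cites an earlier jet-injector study in which the collected fluid "was found to be mainly derived from the fluid that was injected".

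Question (c) is exposed in another way. All the arms compared are jets, so the error is the difference in saline returned between orifices. Since (c) itself asks whether dilution differs by orifice, equal returns cannot be taken for granted.

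**Working it through.** **Inputs.** From the protocol: typical sample 5 µL (3.6); volume SD 1 µL, α = 0.05, β = 0.1, detectable difference 0.84 µL (3.2); minimum n of 20 and 8 (3.2); glucometer SD 0.6 mmol/L (3.2). Assumptions: every value of f (injectate fraction of the tube); mean glucose 5 mmol/L; the two minima pooled to n = 28; 0.6 mmol/L taken as the SD of a single reading.

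**1. The plan's own figure.** Two-sided, two-sample: n = 2 × ((1.960 + 1.282) × 1 / 0.84)² = 29.8, so 30 per intervention. With n = 20 + 8 = 28, the detectable difference is 3.242 × √(2/28) = 0.866 µL and power at 0.84 µL is 88%. So 0.84 µL is consistent with about 28 to 30 per intervention, that is, with both groups combined. Other readings also fit: one-sided gives n = 25, and a paired test with an SD of differences of 1 µL gives n = 15. The point below does not depend on which was used.

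**2. Blood overstated in a tube of given volume.** Overstatement = V × f. With V = 5 µL:

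- f = 5%: 0.25 µL
- f = 10%: 0.50 µL
- f = 16.8%: 0.84 µL (0.84 / 5 = 0.168)
- f = 20%: 1.0 µL

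At f = 16.8%, equal 5 µL tubes from jet and lancet would hide a true blood deficit of 0.84 µL. The protocol does not say whether volume is compared per sample or summed over the four collections. If summed (4 × 5 = 20 µL), 0.84 µL is reached at 0.84 / 20 = 4.2%, and f = 10% adds 2.0 µL.

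**3. Chance of a false result for the jet when blood release is equal.** If both release 5 µL of blood, the jet tube reads 5/(1 − f), an excess of δ = 5/(1 − f) − 5. The probability of a significant difference is about Φ(δ√(n/2)/1 − 1.96).

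| f | δ (µL) | n = 20 (Group 1 alone) | n = 28 (pooled, uncorrected) |
|---|---|---|---|
| 10% | 0.56 | 42% | 55% |
| 15% | 0.88 | 80% | 91% |
| 20% | 1.25 | 98% | 99.7% |

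**4. Noise of a correction in Group 1.** With f = 1 − G(jet)/G(lancet) and f small:

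- Single lancet reading as reference: SD(f) = √2 × 0.6/5 = 0.170, or 0.85 µL on 5 µL.
- Mean of four lancet readings as reference: SD(f) = √1.25 × 0.6/5 = 0.134, or 0.67 µL on 5 µL.

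Added independently to the planned SD of 1 µL, the jet SD becomes √(1 + 0.67²) = 1.20 to √(1 + 0.85²) = 1.31 µL. At the same n, the 0.84 µL difference becomes:

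- Jet against lancet: 0.84 × √((1 + 1.20²)/2) = 0.93 to 0.84 × √((1 + 1.31²)/2) = 0.98 µL.
- Jet against jet: 0.84 × 1.20 = 1.0 to 0.84 × 1.31 = 1.1 µL. This treats the errors as independent; a shared lancet reference would cancel in part.

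These apply the Group 1 noise to every participant. A pooled analysis that includes Group 2's ICG values would be affected differently.

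**The case against.** The strongest reply is that section 3.2 says only that the tube is read in the same way in both groups. It does not say that the raw reading will answer (a) or (c). Group 2's conversion shows that the investigators distinguish sample volume from blood volume. Group 1 collects what a correction needs, and building a derived variable is often left to a SAP. Dilution is also reported in its own right, so a large but dilute sample would be visible. This is a pilot, and nothing is lost if the definition is settled before analysis.

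Much of this stands as mitigation, but it does not remove the point. The protocol goes beyond silence: it fixes the measurement, powers a comparison of volume released on it, and states the conversion for one group only. Followed as written, Group 1 gives a systematically wrong answer to (a). Reporting dilution alongside volume lets a reader suspect this but does not yield a comparison of blood.

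Three stronger readings are tempting, and the protocol does not support them.

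- *That (c) is biased towards the jet injector.* Both sides of that comparison are jets, so no such direction exists.
- *That the whole study lacks a correction.* Group 2 has one.
- *That jet samples will be mostly saline.* The cited study drew interstitial fluid back through the injection orifice in under 0.5 s. Here blood is taken from the skin surface at 10 to 40 s. Its 1% to 3% interstitial share says little about f in this study. Nor does setting 50 µL against 5 µL settle the matter, since 5 µL is one of four samples (about 20 µL in all) and the share of injectate returned is unknown.

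**Conclusion.** The point holds for question (a) in Group 1 and for any volume comparison pooled across groups: uncorrected tube length overstates blood released by the jet relative to the lancet. For question (c) the same gap leaves an error of unknown direction, which is zero if the orifices return equal saline.

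The size depends on f, which the protocol does not give, so the figures are scenarios and not predictions. On a 5 µL tube the overstatement is 0.50 µL at f = 10% and equals the full 0.84 µL at f = 16.8%. The 10% scenario is the dilution difference that Group 1 is sized to detect, so it lies within the range the study was designed to examine. If f turns out close to zero, the error is negligible; the study's own dilution data will show this.

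**What to change.** In sections 3.2 and 3.6, define the volume outcome for questions (a) and (c), in both groups, as blood volume = tube volume × (1 − f), with f = 0 at lancet sites. Take f from ICG in Group 2 and from the jet/lancet glucose ratio in Group 1, preferably as the mean per orifice and time point, with its uncertainty carried into the comparison. Report raw tube volume separately, labelled as fluid collected. State whether the comparison is per sample or summed over the four collections. Restate the 0.84 µL figure as applying to fluid collected, and give a separate, larger figure for blood volume.

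The change uses data already planned and needs no new samples. Its cost is precision. If individual Group 1 readings are used, the correction adds noise with an SD of about 0.67 to 0.85 µL per 5 µL sample (at an assumed 5 mmol/L), which takes the detectable jet-against-lancet difference to about 0.93 to 0.98 µL. Using a mean f avoids erratic individual values but does not remove this uncertainty, which is why it must be carried through. Borrowing Group 2's mean f for Group 1 is possible, but it would rest on only 8 to 10 participants.
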